11.3 Analysis of Primary Safety Endpoint

All analyses described in this section are applicable for C1-INH HAE subjects only. TEAEs will be presented for the following:

- All subjects in the Safety Analysis Set (all subjects on 200 mg CSL312 once monthly, independent of the use of CSL312 200 mg AI or CSL312 200 mg NSD).
- Subjects on 200 mg CSL312 using AI.
- Subjects on 200 mg CSL312 using NSD.

TEAEs will be summarized by the number of subjects and percentage of subjects experiencing at least 1 TEAE, the number of events, as well as the event rates per injection and per subject year.

TEAE rates per injection will be calculated as follows:

$$\text{TEAE Rate per Injection} = \frac{\text{Number of TEAEs}}{\text{Number of injections}}$$

where the number of injections will be the sum of the injections that subjects received during the respective safety evaluation period with the respective device (NSD, AI, or overall) the TEAE is assigned to.

TEAE rates per subject years will be calculated as follows:

$$\text{TEAE Rate per Subject Year} = \frac{\text{Number of TEAEs}}{\text{Subject years}}$$

where subject years will be the sum of the time in years that subjects were exposed to study treatment using that device (NSD, AI, or overall) during the respective safety evaluation period.

An overview summary of TEAEs will be provided including:

- TEAE,
- SAEs,
- Deaths,
- ISRs,
- TEAEs occurring within 24 hours of start of IP administration,
- SAEs occurring within 24 hours of start of IP administration,
- Related TEAEs,
- Related SAEs,
- TEAEs leading to study discontinuation,
- TEAEs in each severity category,
- ISRs, in each severity category,
- TEAEs in each outcome category,
- SAEs in each severity category,
- SAEs in each outcome category,
- AESIs, both as reported by the investigators and as identified via SMQ (see [Section 11.4](#) for definitions).

A summary table by SOC and PT will be provided.

These two summaries will exclude all TEAEs clearly identified to be related to an HAE therapy other than CSL312 during the Follow-up Period. Both summaries will be repeated for TEAEs that can clearly be identified to be related to an HAE therapy medication other than CSL312.

To evaluate the COVID-19 impact on the primary endpoint the overview summary of TEAEs and the summary table by SOC and PT will be repeated as a sensitivity analysis excluding all COVID-19 related TEAEs (per the corresponding SMQ).

The TEAEs will be presented in a by-subject listing. TEAEs clearly identified to be related to an HAE therapy other than CSL312 will be included and flagged.

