The important potential risks of TEEs and abnormal bleeding were removed from the CSL312 list of safety concerns following the review of recently accumulated clinical study data (CSL312_1001, CSL312_1003, CSL312_2001, and CSL312_COVID-19) together with nonclinical data and scientific literature; although TEEs and abnormal bleeding are no longer considered potential risks, safety surveillance and monitoring of these types of events as AESIs will continue in accordance with existing protocol provisions in the CSL312_3002 clinical study (additional information is provided in the CSL312 Investigator's Brochure).

Given the potential benefits of CSL312 for subjects with HAE, as well as the favorable safety data of CSL312 from phase 1 studies in healthy volunteers (CSL312_1001, CSL312_1003, and CSL312_1004), in the phase 2 and 3 studies in subjects with HAE (CSL312_2001, CSL312_3001, and CSL312_3002), and in the phase 2 study in subjects with severe COVID-19 (CSL312_COVID-19), and taking into account the implementation of procedures in the current study to closely monitor subject safety, the associated benefit / risk assessment is considered to be acceptable. Additional information on CSL312 is provided in the CSL312 Investigator's Brochure.

2 Study Objectives and Endpoints

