4.4 Determination of the Sample Size

Approximately 150 subjects (including 8 Japanese subjects) are planned to be enrolled into the study and a minimum of 100 subjects are planned to receive treatment for a minimum of 12 months.

This is a single arm study without a control arm. The sample size for this single arm, open-label study is not based on a formal statistical sample size calculation but on the guideline E1A issued by the International Conference on Harmonisation, March 1995. The sample size of 100 subjects allows observation of ≥ 1 AE with a probability of 3% at 95% confidence.

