Wilson confidence intervals will be used to calculate the CIs for percentages.

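### The primary safety endpoint, SAEs, deaths and AESIs are planned without confidence intervals, so a zero-event AESI row would not show what risk it excludes

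*SAP*

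**What the plan says.** **Safety.** SAP 11.3 begins the list of summary measures with "TEAEs will be summarized by the number of subjects and percentage of subjects experiencing at least 1 TEAE, the number of events" and completes it with "the number of events, as well as the event rates per injection and per subject year". SAEs, deaths, related TEAEs and AESIs are rows of the same overview, shown overall and for each device (AI, NSD). SAP 11.4 applies these measures to the secondary safety tables. SAP Table 2 and Protocol 2.2.2 list only counts and percentages for the secondary safety endpoints. SAP 7 does not fill the gap: its default summary has a 95% CI for continuous variables but only frequencies and percentages for categorical ones.

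**Efficacy.** Responder and attack-free percentages get 95% CIs, and SAP 10.2.1.2 closes with "Wilson confidence intervals will be used to calculate the CIs for percentages". Cumulative SGART and IGART percentages also get 95% CIs (SAP 10.2.1.5 and 10.3.2.1).

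**Sample size.** SAP 4.4 says the size "is not based on a formal statistical sample size calculation but on the guideline E1A issued by the International Conference on Harmonisation, March 1995". It then gives one numerical property: "The sample size of 100 subjects allows observation of ≥ 1 AE with a probability of 3% at 95% confidence". On enrolment it states "Approximately 150 subjects (including 8 Japanese subjects) are planned to be enrolled into the study". Of these, at least 100 should be treated for 12 months or longer. Protocol 10.1 has the same basis and the same sentence.

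**The concern.** The primary objective is long-term safety, yet the primary result would carry no statement of precision, while secondary and exploratory efficacy percentages would. For any TEAE this matters little, because that percentage is likely to be high. It matters for rare, important rows: thromboembolic events, abnormal bleeding, severe hypersensitivity, SAEs and deaths. There a table entry of 0 (0.0%) is a plausible outcome, and on its own it says nothing about the size of risk that the data exclude. The sample size is supported by exactly this kind of limit, but the tables do not report it.

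**Working it through.** **Inputs.** From SAP 4.4: 100 subjects as the minimum treated for 12 months, about 150 enrolled, 8 of them Japanese, and the 3%/95% property. From SAP 6.3 and 11.2: percentages use the Safety Analysis Set, which is everyone in the ATS set with at least one dose. About 150 is therefore the relevant planned denominator, and 100 is a lower reference. The true risks of 0.5%, 1% and 2% are assumptions; the documents give none.

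**1. The plan's own figure.** P(at least one case) = 1 − (1 − p)^n. With n = 100 and p = 0.03, this is 1 − 0.97^100 = 0.952, which matches the stated 95%. The n required is ln(0.05)/ln(0.97) = 98.4, so 99 against 100 stated.

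**2. Link to an upper bound.** Solving (1 − p)^100 = 0.05 gives p = 1 − 0.05^(1/100) = 2.95%. This is the one-sided 95% upper limit when 0 of 100 subjects have the event. The detection statement and the zero-event bound are one calculation.

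**3. Chance of seeing no case, (1 − p)^n.**

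| Assumed true risk | n = 150 | n = 100 |
|---|---|---|
| 0.5% | 0.995^150 = 47.1% | 0.995^100 = 60.6% |
| 1% | 0.99^150 = 22.1% | 0.99^100 = 36.6% |
| 2% | 0.98^150 = 4.8% | 0.98^100 = 13.3% |

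The documents do not say how many subjects each device column will hold. If one held 75 (assumption), a 1% risk would show no case 0.99^75 = 47.1% of the time.

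**4. What a zero row would show with an interval.** The exact two-sided 95% upper limit is 1 − 0.025^(1/n).

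- 0/150: 1 − 0.025^(1/150) = 2.4%
- 0/100: 1 − 0.025^(1/100) = 3.6%
- 0/8 (planned Japanese subjects): 1 − 0.025^(1/8) = 36.9%

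A Wilson limit at zero events, z²/(n + z²), gives 2.5% for 0/150 and 3.7% for 0/100, so the choice of method matters little here. One case in 150 (0.7%) has an exact 95% CI of 0.02% to 3.7%.

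**5. The exposure-adjusted rate.** With no events, the exact two-sided 95% Poisson upper limit is −ln(0.025)/T = 3.69/T for T subject-years. At the planned minimum of 100 subjects × 1 year, T = 100 and the limit is 3.7 per 100 subject-years. It falls in proportion as exposure grows.

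**The case against.** The strongest reply is that the study is descriptive and tests no hypothesis, and that a reader can derive a limit from the printed count and denominator. Rare AESIs are also handled case by case: SMQ searches in addition to investigator reports, listings, expedited reporting, IDMC review and halting criteria. No rule in either document turns zero events into a conclusion of safety. All of this is true, and it limits the point to reporting. It does not remove it, because an interval is estimation and not a test, and the plan already gives intervals to efficacy percentages that it calls exploratory. The case-level safeguards find events; they do not say what risk remains when none is found.

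Second, percentages ignore unequal follow-up. Treatment duration varies by subject, and the Amendment 1 schedule runs to Month 42. This stands, so the rate per subject year needs an interval as well.

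Four stronger readings are tempting, and the documents do not support them.

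- **The sample size rests solely on the 3% bound.** Both documents name guideline E1A as the basis; the bound is only the sole quantitative justification.
- **A 1% risk would be missed 37% of the time.** That uses the 12-month minimum of 100, not the Safety Analysis Set.
- **Protocol 1.4 already infers absence of risk from absence of events.** It does say "although TEEs and abnormal bleeding are no longer considered potential risks", but it cites other studies together with nonclinical data and literature, refers to the Investigator's Brochure, and continues AESI monitoring.
- **The sample-size sentence is wrong.** It is loosely worded, but read as an AE with a 3% probability its figures are correct.

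**Conclusion.** The point holds as a reporting gap and is a cheap improvement. Followed as written, the plan gives a primary safety result and AESI results with no measure of precision. With about 150 treated subjects, a zero-event AESI row would be compatible with a risk of up to 2.4%, and the table would not show it. An assumed 1% risk would produce that row 22% of the time, with a range of 47% to 5% for assumed risks of 0.5% to 2%. These figures assume independent subjects and treat risk as cumulative over each subject's observed follow-up.

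A reader might go further and infer that the study cannot tell zero risk from any risk of 1% or more. It can exclude the larger ones: at n = 150, a 2% risk would show no case 4.8% of the time and a 3% risk about 1% (0.97^150). Nor is any planned estimate biased or wrong.

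**What to change.** In SAP 11.3 and 11.4:

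- Add exact (Clopper-Pearson) two-sided 95% CIs to the subject percentages for SAEs, deaths, related TEAEs and each AESI category, in the overall, AI and NSD columns. Print the upper limit when the count is zero.
- Add a 95% CI to the rate per subject year in the same rows. Use exact Poisson limits when there are no events or at most one per subject; otherwise use a method that allows for repeated events within a subject.
- State that AESI conclusions in the CSR will be worded from the upper limit.

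Optionally, reword the sample-size sentence in SAP 4.4 to say that an AE with a true incidence of 3% is seen at least once with 95% probability in 100 subjects. This is editorial.

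The cost is SAP text, a few table columns and a little programming, with no new data and no design change. The downside is that zero-event rows look less reassuring. If the database is already locked, the intervals can be added and disclosed in the CSR, where SAP 3 places deviations from the plan.

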- Subcutaneous administration of CSL312 dose by investigator or delegate (after completion of physical examination and vital signs). For CSL312 naïve subjects, the first dose of CSL312 will be a loading dose consisting of 2 SC injections of 200 mg CSL312 each for a total dose of 400 mg CSL312. Subjects rolling over from Studies CSL312_3001 and CSL312_2001 will not receive a loading dose. Subjects will complete the Medication Dosing Diary on the eDiary after dosing at the site is complete.
- Record concomitant medications and therapies (type, dose, route, date, and time).
- Record AEs.

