8.2.6 Actual and Planned Treatment

Both planned vial numbers integrated from the Interactive Response Technology (IRT) and the actual administered vial numbers will be collected via eCRF. If a subject's actual treatment is the same as the assigned treatment, then actual treatment is the assigned treatment.

The planned treatment for all subjects is 200 mg. Efficacy outputs will be displayed by planned treatment of 200 mg. For details on the derivation of efficacy variables see [Section 10.2.1](#).

The 400 mg loading dose for CSL312 naïve subjects is considered a single injection and a regular part of the planned 200 mg treatment regimen. AEs where the most recent dose was the loading dose will be flagged in listings of AEs.

In case of unexpected deviations from planned treatment including undefined dose modifications, overdoses and other deviations, an evaluation of that case and a final decision under what actual dose the subject should be presented for analysis will be done before DBL in the PARM.

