8.4 Study Periods Relative to Treatment

AEs, HAE attacks, laboratory data, vital signs and other measurements will be assigned to the study time periods defined below.

Table 3 Definitions of Study Periods Relative to Treatment

Period	Start Date	End Date
Screening Period	Date of Informed Consent	Run-in Period Start Date
Run-in Period	Run-in Period Start Date	Day 1 Visit date of the Treatment Period or Date of Run-in Non-completion [whichever is first]
Treatment/Efficacy evaluation period	Date of Day 1 Visit of Treatment Period	Date of EOT Visit or EOS date [whichever is first]
Treatment/Efficacy before transition to AI evaluation period	Date of Day 1 Visit of Treatment Period	Date of first dose with AI – 1 Day (see Section 8.2.1)
Treatment/Efficacy after transition to AI evaluation period	Date of first dose with AI (see Section 8.2.1)	Date of EOT Visit or EOS date [whichever is first]
Follow-up	Date of EOT Visit	Date of Final/ Follow-up Visit
Safety evaluation period	Date and start time of First CSL312 Administration as entered in the eDiary	Date of Final/ Follow-up Visit
Safety Evaluation before transition to AI evaluation period	Date and start time of First CSL312 Administration as entered in the eDiary	Date of first dose with AI – 1 Day (see Section 8.2.1)
Safety Evaluation after transition to AI evaluation period	Date of first dose with AI (see Section 8.2.1)	Date of Final/ Follow-up Visit

The EOS date is the date entered in the Conclusion of Subject Participation eCRF page and should generally be identical to the date of the Follow-up Visit.

The handling of any unplanned dose changes or device changes will be discussed in the PARM. The safety evaluation period consists of the Treatment/Efficacy evaluation period plus the Follow-up Period.

Screening and Run-in periods will not be performed for roll-over subjects, instead relevant endpoint data (such as HAE attacks during the Run-in period) will be used from the CSL312_2001 and CSL312_3001 studies.

The duration of the Efficacy evaluation and the Safety evaluation period in days will be calculated as:

End Date – Start Date + 1 Day.

Screening, Run-in and Follow-up periods in days will be calculated as:

End Date – Start Date.

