11.1 Extent of Exposure

Exposure to the IP will be summarized descriptively, including the following:

- Duration of exposure [months], calculated as exposure in days/30.4375, using NSD, AI, and overall,
- Duration of exposure [years], calculated as exposure in days/365.25, using NSD, AI, and overall,
- Number of injections,

- Total cumulative number of injections,
- Number of subjects transitioned to AI,
- Number of subjects with more than 12, 15, 18, 21, ... (3-month increments) months of exposure during NSD use, during AI use, and overall,
- Number of subjects with more than 12, 15, 18, 21, ... (3-injection increments) injections using NSD, using AI, and overall,
- Total cumulative dose received [mg],
- Total subject years of exposure.

The listing of individual subject data will include all variables presented in the summary tables. The same listing will include overall compliance and the planned number of injections (see [Section 10.6](#) for derivation).

An additional listing by subject and by injection will show all injection details from the subject diary: date, start time, end time, number of syringes and whether the injection was in the abdomen (yes/no). Any issue with the injections recorded on the Device Event page of the eCRF will be included in this listing as well. Bar charts will be produced for the duration of exposure in months and the number of injections, by injection device and overall.

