11.2 Adverse Events – Coding and Definitions

TEAEs are AEs which start on or after the date and time of the first administration of study treatment. TEAEs occurring until the Follow-up Visit will be summarized.

Where AE start dates and/or times are missing or partially missing, AEs will be assumed to be treatment-emergent, except if the partial start dates and/or times or the AE end date and/or time indicate that the AE started before the first administration of IP.

Table 4 TEAE Assignment in Case of Missing AE Start Date Elements

Missing elements of AE start	Rule	
Regardless of any missing information for AE start: AE end date / time < first IP start date / time		non-TEAE
Otherwise (ie, if AE end date / time \geq first IP start date / time or AE end date is missing, or AE is ongoing)		
- all		TEAE
- day and month	AE start year \geq IP start year	TEAE
	AE start year < IP start year	non-TEAE
- day	AE start month / year \geq IP start month / year	TEAE
	AE start month / year < IP start month / year	non-TEAE
- time	AE start date \geq IP start date	TEAE
	AE start date < IP start date	non-TEAE

Similarly, for subjects who transitioned to AI, where start dates and/or times of a TEAE are missing will be assumed to be on AI, except if the partial start dates and/or times or the AE end date and/or time indicate that the AE started before first dose with AI. The AI reference date/time will be used instead of the IP start date/time (see [Section 8.2.1](#)).

All reported AEs regardless of when they occurred will be listed.

COVID-19 associated AEs will be identified using the COVID-19 SMQ and will generally be included in TEAE tables identified by their standard MedDRA coding.

If for a TEAE the relationship to study treatment is missing the worst case will be assumed for summarizing analysis (ie, the relationship to study treatment will be assumed to be “Yes”). If the AE or SAE with missing relationship started before the first injection of study treatment it will be considered as “not related” (realistic case). No other imputations for missing AE information will be done.

AEs will be coded using MedDRA. There will be periodic updates of the MedDRA version. The latest licensed version will be used, and version updates will be implemented upon availability. AEs will be primarily classified by MedDRA PT. Analyses will be performed by SOC and PT. Aggregated incidences at SOC level and any TEAE will also be provided.

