11.4 Analysis of Secondary Endpoints based on Adverse Events

The analysis for the primary endpoints described in [Section 11.3](#) will be repeated for the nC1-INH subjects, without the exclusion of TEAEs clearly identified to be related to an HAE therapy other than CSL312 and excluding the tables and listings associated with COVID-19.

The following summary tables will be provided for all subjects (C1-INH and nC1-INH) in the Safety Analysis Set, without excluding TEAEs clearly identified to be related to a HAE therapy other than CSL312:

- Overview table of TEAEs (same items as described in [Section 11.3](#)).
- Overview table of SAEs (same as above, restricted to SAEs).
- SAEs by SOC and PT.
- TEAEs by severity, SOC and PT.
- Related TEAEs by SOC and PT.
- TEAEs leading to study discontinuation by SOC and PT.
- TEAEs by 3-month windows. Rates will still be based on the cumulative safety period. Assignment of TEAEs to 3-month windows will be based on the start date of the AE, similarly as for HAE attacks (see [Section 10.2.1](#)). Unclear assignments due to incomplete AE start dates will be discussed during the PARM.
- AESI by SOC and PT as identified via SMQ (definition of AESI as in [Section 11.2](#)).
- Non-serious TEAEs by SOC and PT.
- Laboratory Findings reported as AEs.
- Anti-CSL312 antibodies.

Summary tables will be presented for the following:

- All subjects in the Safety Analysis Set (all subjects on 200 mg CSL312 once monthly, independent of the use of CSL312 200 mg AI or CSL312 200 mg NSD).
- Subjects on 200 mg CSL312 using AI.
- Subjects on 200 mg CSL312 using NSD.

TEAEs will be summarized by the number of subjects and percentage of subjects experiencing at least 1 TEAE, the number of events, as well as the event rates per injection and per subject year calculated in the same manner as for the primary endpoint described in [Section 11.3](#).

The following listings will be provided:

- Non TEAEs.
- TEAEs.
- TEAEs for Japanese subjects.
- TEAEs for adolescents.
- SAEs.
- SAEs with fatal outcome.
- AEs leading to study withdrawal.
- AEs leading to permanent discontinuation of study treatment.
- AESIs.
- Related AEs.
- TEAEs related to laboratory findings.
- AEs related to COVID-19.

TEAEs clearly identified to be related to an HAE therapy other than CSL312 will be flagged in listings.

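### Primary-endpoint TEAE rates: events run to the Follow-up Visit, but the per-injection denominators do not match that window and the per-subject-year denominator has no defined end

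*SAP*

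**What the plan says.** - **Event window.** SAP 11.2: "TEAEs occurring until the Follow-up Visit will be summarized". Protocol 3.4 sets Follow-up at 2 months after the End of Treatment Visit, which is itself 1 month after the last dose. From the primary summaries SAP 11.3 drops one group: "These two summaries will exclude all TEAEs clearly identified to be related to an HAE therapy other than CSL312 during the Follow-up Period".
- **Time denominator.** SAP 11.3 defines subject-years as "the sum of the time in years that subjects were exposed to study treatment using that device", and the sentence goes on to tie this to the respective safety evaluation period. SAP 8.4: "The safety evaluation period consists of the Treatment/Efficacy evaluation period plus the Follow-up Period". SAP 11.1 gives only a unit conversion: "Duration of exposure [months], calculated as exposure in days/30.4375, using NSD, AI, and overall". It sets no start or end date. For TEAEs by 3-month window, SAP 11.4 says: "Rates will still be based on the cumulative safety period".
- **Injection denominator.** SAP 11.3 sums the injections received with the device. SAP 8.2.6 says that the 400 mg loading dose for CSL312-naïve "subjects is considered a single injection and a regular part of the planned 200 mg treatment regimen". Protocol 8.6.3.1 says that for these subjects "the first dose of CSL312 will be a loading dose consisting of 2 SC injections of 200 mg CSL312 each".
- **Device assignment.** SAP 7.1 assigns an AE to the device in use when it started. In SAP Table 3 the pre-transition safety period ends the day before the first AI dose, and the post-transition period runs to the Final/Follow-up Visit. Switching is possible only from Month 12 (Protocol 8.6.6.1).
- **Percentages.** SAP 11.2 bases subject incidence on the Safety Analysis Set, with no restriction for the device columns.

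**The concern.** A rate is interpretable only if its events and its denominator cover the same window. Here the events include a follow-up stretch in which nobody is injected. For switchers that stretch belongs wholly to one device, and whether it enters the time denominator is unclear. The loading dose also makes the injection count smaller than the number of injections given.

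These descriptive rates are themselves the primary endpoint summary, so no later test absorbs the error. The AI and NSD columns will be read side by side, and an accounting artefact could look like a device effect. Injection site reactions are in the primary overview, so the injection count bears directly on how those events are read. Two programmers could also follow SAP 11.3 faithfully and report different subject-year rates.

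**Working it through.** **The plan's own figures.** The plan states no TEAE rate to reproduce. Its one sample-size statement does reproduce: 1 − 0.97^100 = 0.952 against the stated 95%. It is not affected by this point.

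**Inputs.** Follow-up is 2 months after End of Treatment (Protocol 3.4). End of Treatment is 1 month after the last dose (Schedule of Assessments). Dosing is monthly, so T months on a device means T injections. Assumptions: a constant AE hazard, the time on AI, and the share of naïve subjects. The documents give none of these.

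**(a) Per injection, follow-up.** A switcher's NSD period has no follow-up, so each NSD injection carries 1 month of events. The AI period carries T + 2 months of events over T injections.

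| AI months T | AI/NSD ratio (T + 2)/T |
|---|---|
| 6 | 8/6 = 1.33 |
| 12 | 14/12 = 1.17 |
| 24 | 26/24 = 1.08 |

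The overall column rises too: with 12 NSD and 6 AI months, 20/18 = 1.11; with 12 and 12, 26/24 = 1.08. No definition of exposure changes this, because exposure time is not in the formula. Amendment 1 allows the follow-up call up to 14 days early, so about 46 days instead of 60. At 6 AI months (6 × 30.4375 = 182.6 days) the excess is then 46/182.6 = 25% instead of 33%.

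**(b) Per injection, loading dose.** A naïve subject with 12 doses receives 13 injections and is counted with 12: 13/12 = 1.083, about 8% too high. Over 150 subjects the shortfall runs from 50/(150 × 30) = 1.1% (50 naïve, 30 doses each) to 70/(150 × 12) = 3.9% (70 naïve, 12 doses each). Loading doses precede any switch, so this affects only the NSD and overall columns. It works in the opposite direction to (a) in a device display.

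**(c) Per subject-year.** The result depends on where exposure ends:

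| End of exposure | Factor | 12 months | 30 months |
|---|---|---|---|
| Follow-up (whole safety period) | (T + 2)/(T + 2) | 1.00 | 1.00 |
| End of Treatment | (T + 2)/T | 14/12 = 1.17 | 32/30 = 1.07 |
| Last dose | (T + 2)/(T − 1) | 14/11 = 1.27 | 32/29 = 1.10 |

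**(d) Percentages.** If the whole Safety Analysis Set is used literally under the AI heading, AI incidence is multiplied by (AI users)/(all treated). The documents do not give the number of switchers, so the size is unknown.

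**The case against.** The strongest reply concerns the time denominator. A reader might infer that SAP 11.3 divides by on-treatment time and that the primary subject-year rates are therefore overstated. The documents do not support that. The sentence refers to the safety evaluation period, SAP 8.4 includes Follow-up in that period, Table 3 gives it separate limits before and after the switch to AI, and the remark in SAP 11.4 suggests that the safety period is already the intended base. What stands is a missing definition that permits a mismatch. Nor do the documents say that SAP 11.1 and 11.3 must share one exposure variable.

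A reader might also infer that every follow-up event of a switcher lands on AI in the primary summaries. That goes too far, because events clearly due to another HAE therapy are removed. The rule is narrow, however: SAP 11.2 limits it to injection site reactions starting within 72 hours of another HAE medication. Assigning post-treatment events to the last device is reasonable in itself, and subjects who never switch keep theirs under NSD. The difficulty is that per injection nothing in the denominator matches those events.

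Counting the loading dose once is a disclosed convention, and its overall effect is small. But the rule in SAP 8.2.6 is general, the compliance rule in SAP 10.6 is stated separately, and SAP 11.3 makes no exception. The result is a rate per dosing occasion labelled as a rate per injection.

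Follow-up AEs under Amendment 1 come from one telephone contact and may be under-reported, which would shrink (a). No device hypothesis is tested, so a matched comparison in switchers is optional and is not needed to correct the plan.

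**Conclusion.** The point holds for the per-injection rates and as a missing definition for the subject-year rates. Per injection, a switcher's AI rate is raised relative to NSD by 33%, 17% and 8% at 6, 12 and 24 AI months, apart from the few events that the other-therapy rule removes. The loading-dose count adds about 8% for a naïve subject with 12 doses, or about 1–4% overall if 50–70 of 150 subjects are naïve, all in the NSD and overall columns. Per subject-year the excess lies between nil and 17% at 12 months (nil and 7% at 30) according to whether exposure runs to Follow-up or stops at End of Treatment; an overstatement is possible but not shown. All these sizes rest on a constant hazard and on assumed AI durations and naïve share. The AI percentage denominator needs one clarifying line.

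This should be corrected before database lock, because it concerns the primary endpoint and costs little. It does not show that the plan sets out to compare devices.

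**What to change.** 1. Use one window for events and time in each column of the subject-year tables. Overall: first dose to Follow-up for both. Device columns: end both at End of Treatment, and show later events with their own person-time in a separate Follow-up column. Do not move the events and keep the time: that would bias the AI rate low by T/(T + 2), for example 6/8 = 0.75 at 6 AI months.
2. Limit per-injection rates to events up to End of Treatment.
3. Count the loading dose as 2 injections in per-injection rates. The diary records the number of syringes (SAP 11.1). Leave the compliance rule in SAP 10.6 as it is.
4. Use subjects with at least 1 AI dose as the AI percentage denominator.
5. Define duration of exposure in SAP 11.1 separately, with start and end dates per device. Otherwise the counts of subjects with more than 12 months of exposure could include 2 off-treatment months.
6. State that the AI and NSD columns are not a device comparison: AI starts only from Month 12, so the NSD column holds first doses and early dropouts and the AI column only those who stayed. A switcher-only contrast is optional.

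Cost: SAP wording and one added Follow-up column. The downside is slightly fewer events in the device columns.
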